### **8.2.2. Clinical Study Report**

The unexpected adverse events and serious adverse events occurring during the study will be discussed in the safety evaluation part of the Clinical Study Report.

## **9. RECORDING OF DATA AND SOURCE VERIFICATION**

### **9.1. Case Report Forms (CRFs)**

Case report forms (CRF) will be provided for the recording of all data. Data will be recorded directly and legibly onto the record forms, in blue/black ink. The signature of the investigator will attest the accuracy of the data on each CRF. If any assessments are omitted, the reason for such omissions will be noted on the CRFs. Corrections, with the reason for the corrections if applicable, should be made legibly, dated and initialled. Correction fluid is not allowed. There are three CRFs in total for each participant in this study, except for stimulant-naïve participant later included in the drug-group, who will have four CRFs.

## **9.2. Source data**

The medical records for each patient should contain information that is important for the patient's safety and continued care and to fulfil the requirement that critical study data should be verifiable. To achieve this, the medical records of each patient should clearly describe at least:

- Dates for tests in relation to the study and scores on ASRS
- Date of, and reason for, withdrawal from study

## **9.3. Archiving and storage of study documents**

Patient files shall be kept for the maximum period of time permitted by each hospital. The code list for patient identification and the study documentation (CRFs, Site File etc.) shall be retained and stored according to instructions from the Regional Ethics Committee. All information concerning the study will be stored in a safe place inaccessible to unauthorized personnel.

# **10. STATISTICAL CONSIDERATIONS**

## **10.1. Determination of sample size**

To assess the required number of participants, a power analysis was calculated on the basis of literature indicating the similar DBT-group intervention in a smaller study showed a significant reduction in ADHD measures in the skills training group (n=19) compared to the control group (n=18) (Hirvikoski et al 2011). To address the hypothesis of superiority of the DBT-based group treatment on different outcome measures and an assumed difference in at least 10% between means (and SD 15%) of the two independent groups, we estimated a need of sample size of about 50 participants in each group (alpha = .05, power = .9) (<https://clincalc.com/stats/samplesize.aspx>). To account for dropouts up to 20%, more patients are needed, resulting in a total of 120 participants.

## **10.2. Randomisation**

Participants are randomly allocated (ratio 1:1) to either the active DBT-bGT or the control TAU condition by a blinded lottery procedure at each site. This manual procedure of randomization method is suitable to randomize participants into groups that result in equal sample sizes, and is used to ensure a balance in sample size across groups over time.

At each site, clinicians are recruiting patients for the study. Patients who consent to participate are assigned a unique number by the study administrator at the site, entering it to a key code list. When the list is fully subscribed with a sufficient number of participants to form two groups, all the numbers are written on a folded piece of paper, and placed in a container. Then, under supervision and by a lottery procedure, one number at a time is drawn by an independent person every second time to the DBTgroup and the TAU-goup respectively. The draw takes place blindly for the participant and the person who draws and the monitor. Afterwards, when all the numbers have been drawn and assigned to their group, are the numbers with corresponding name and group announced so that the participants get to know which group they shall belong to in the study.

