##### **3.2.1. All participants**

For eligibility the prospective participants at screening prior to receiving the study intervention must meet all of the following conditions:

- Clinically diagnosed with ADHD according to DSM-IV. Diagnostic assessment is part of standard diagnostic procedures at the clinics, which include confirmatory assessment by a specialist in psychiatry or psychology
- On stable treatment with ADHD medication or off medication.
- Must be between the ages of 18 and 60.
- Signed informed consent and expected cooperation of the patients for the intervention and the questionnaires must be obtained and documented according to International Conference on Harmonization, Good Clinical Practice and national/local regulations.

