### **3.3. Exclusion criteria**

[figure not shown]
Any participant (from either of the three groups) will be excluded from the study if ongoing psychiatric disorders and/or psychosocial factors are considered to clearly interfere with the patients' motivation or ability to participate in the group therapy, and if they meet any of the following criteria:

- Any psychotic disorder
- Recently suicidal behaviour
- Substance or alcohol abuse or dependence within three months prior to screening for inclusion
- Pervasive developmental disorder
- Intellectual disability
- Seizures or any neurological diseases causing mental handicap

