## **5.3. Concomitant medication**

Treatment with the following groups of pharmacological agents will be recorded in the case report form (CRF), but is not considered as any exclusion criteria for participation. It is however recommended that the dose be kept stable during participation in the study, and for inclusion it must have been at least 6 weeks after the last dose change of drug treatment.

- ADHD medication (centralstimulants or non-stimulants)
- Other psychopharmaca

Alcohol or substance abuse will be screened for alcohol- and substance-problems; The Alcohol Use Disorder Identification Test (AUDIT) and The Drug Use Disorder Identification Test (DUDIT).

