### **6.4. Criteria for patient discontinuation**

Patients may be discontinued from study treatment and assessments at any time. Specific reasons for discontinuing a patient for this study are:

- Voluntary discontinuation by the patient who is at any time free to discontinue his/her participation in the study, without prejudice to further treatment.
- Safety reason as judged by the Principal Investigator.
- Incorrect enrollment (i.e. the patient does not meet the required inclusion/exclusion criteria for the study)
- Related Serious Adverse Event

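### Eligibility is checked before a wait of unstated length, is not re-confirmed at the lottery, and can be acted on after allocation is known

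*Protocol*

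**What the plan says.** Eligibility is dated in three ways.

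- **Inclusion criteria (Protocol 3.2.1).** The rule is that "prospective participants at screening prior to receiving the study intervention must meet all of the following conditions". One of these conditions is "On stable treatment with ADHD medication or off medication".
- **Exclusion criteria (Protocol 3.3).** The substance criterion reads "Substance or alcohol abuse or dependence within three months prior to screening for inclusion". The suicidal-behaviour criterion is limited to recent behaviour but has no reference date.
- **Medication (Protocol 5.3).** The requirement is that "for inclusion it must have been at least 6 weeks after the last dose change of drug treatment". Inclusion is not defined as listing, consent or the draw. After entry, stability is only advised: "It is however recommended that the dose be kept stable during participation in the study".

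Randomisation (Protocol 10.2) is done in batches at each site. Consenting patients get a number and go on a list. The lottery takes place "When the list is fully subscribed with a sufficient number of participants to form two groups". Afterwards the allocation is announced to the participants. The section sets no limit on the wait and asks for no check of eligibility before the numbers go into the container.

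Protocol 6.4 allows patients to be discontinued from both treatment and assessments at any time. One listed reason is "Incorrect enrollment (i.e. the patient does not meet the required inclusion/exclusion criteria for the study". Protocol 10.3 analyses, for each questionnaire, only the participants who answered it.

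**The concern.** There are two separate consequences.

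The first is who gets randomised. The protocol describes a population that is unmedicated or stably medicated and free of recent substance abuse. A patient can meet that description at screening, have a new event while listed, and still be drawn, because no step before the draw looks for it.

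The second is more important. If the event is noticed later, the decision about that patient is made after allocation is known. Section 6.4 permits an eligibility-based removal that ends assessments as well as treatment. Under Section 10.3, anyone removed before the post-treatment questionnaire is lost from the primary comparison. If removals are more likely in one arm, the groups compared are no longer the groups that were randomised.

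**Working it through.** The plan gives no figure on this point, so there is none to reproduce. The check has two parts: how long the wait could be, and what the text allows at each step.

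**Length of the wait (illustration)**

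Inputs from the protocol:
- about 120 participants (3.2);
- recruitment of one year, or about 13 months from December 2015 to 31/12/2016 (Section 4), that is 52 to 56.5 weeks;
- groups of 7 to 10 (3.2) or 7 to 9 (5.1), so two groups need a list of L = 14 to 20 or 14 to 18.

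Assumptions: S equal sites and even accrual. The protocol says multicentre but gives no number of sites.

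Formulas: interval between patients at a site = weeks × S / 120; wait of the first patient listed = interval × (L − 1); mean wait = interval × (L − 1) / 2.

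| Sites (assumed) | Weeks, L | Interval (weeks) | First patient waits (weeks) | Mean wait (weeks) | Share waiting over 6 weeks |
|---|---|---|---|---|---|
| 2 | 52, 14 | 52 × 2/120 = 0.867 | 0.867 × 13 = 11.3 | 0.867 × 6.5 = 5.6 | 7/14 = 50% |
| 2 | 56.5, 20 | 56.5 × 2/120 = 0.942 | 0.942 × 19 = 17.9 | 0.942 × 9.5 = 8.9 | 13/20 = 65% |
| 4 | 52, 14 | 52 × 4/120 = 1.733 | 1.733 × 13 = 22.5 | 1.733 × 6.5 = 11.3 | 10/14 = 71% |
| 4 | 56.5, 20 | 56.5 × 4/120 = 1.883 | 1.883 × 19 = 35.8 | 1.883 × 9.5 = 17.9 | 16/20 = 80% |

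Under these assumptions, waits of weeks to months are plausible. This shows only that there is time for a new event. It does not count ineligible patients.

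**What the text allows at each step**

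1. *During the wait.* Both windows are minimum clean periods. A patient with no new event only moves further from the last dose change or last abuse. Eligibility is lost only through a new event.
2. *At the draw.* Everyone on a list is drawn together by lottery. A patient with a new event is as likely to go to one arm as to the other, so the allocation stays unbiased.
3. *After the draw.* DBT-bGT patients meet two therapists weekly and have individual coaching after each session (5.1). TAU is not standardised and varies by patient and clinic (5.2). Section 3.3 also asks whether problems interfere with taking part in the group therapy, and during the controlled 14 weeks only one arm puts that to the test. The chance that a problem is noticed and acted on therefore differs by arm.
4. *In the analysis.* Removal under 6.4 can end assessments, and 10.3 then drops the patient. With 120/2 = 60 per arm, each such removal is 1/60 = 1.7% of an arm.

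**The case against.** **Waiting does not make eligibility expire.** A reader might infer from the batch draw that the 6-week and 3-month windows run out while patients wait, or might set the length of the wait against the length of the windows. The documents do not support this. Both are minimum clean periods, so the comparison says nothing about eligibility. Nor does the wait always exceed 6 weeks: with 2 sites, a list of 14 and 52 weeks, the mean is 5.6. This objection stands in full.

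**No event rate is given.** Section 1.1 cites 25 to 50% lack of continuity in medication use after about one year, and a reader might turn that into a number of patients. It comes from other cohorts, whereas this trial admits patients who are stable on medication or off it. No count follows.

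**The text is less fixed at screening than it looks.** Only the substance criterion is expressly counted back from screening. The suicidal-behaviour criterion is undated, and inclusion in 5.3 could be read as the day of the draw. A patient who met the criteria at screening and changed later is arguably not an incorrect enrolment at all. This is fair, but it leaves the matter open: sites may read the rule either way, and they would do so after allocation is known.

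**A dose change just before the draw differs little from one just after it,** which the protocol tolerates and records. This also stands, and it limits the first consequence.

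**Section 10.3 excludes nobody on eligibility grounds.** That is true. The loss comes indirectly, through ended assessments combined with analysis of responders only.

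**Conclusion.** The point holds in a limited form. The protocol checks eligibility at screening or at an undefined inclusion, lets patients wait without a stated limit, and has no re-check before the lottery. A patient with a new event while listed can therefore be randomised. That affects the population studied and adds noise. A reader might infer that the lottery itself is biased, but it is not, because such events fall on both arms by chance.

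The bias risk lies after the draw, in the combination of eligibility-based removal from assessments (6.4), analysis of responders only (10.3) and unequal contact between arms in an open trial. The protocol permits one-sided removal; nothing in it shows that this will happen.

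The number affected cannot be stated. The waits shown rest on an assumed number of sites and even accrual, and the documents give no event rate. The correction is worth making because it is cheap and acts before allocation is known.

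**What to change.** - **Section 10.2:** have each site re-confirm the protocol's existing eligibility criteria shortly before the numbers go into the container. Anyone no longer eligible comes off the list before the draw and may join a later list if the criteria are met again.
- **Sections 3.2.1, 3.3 and 5.3:** define inclusion, and reconcile the reference date of the existing windows with the date of the draw. The length of the windows is not at issue and stays as it is.
- **Sections 6.4 and 10.3:** state that once drawn, a patient may stop treatment but is still assessed, subject to continuing consent, and analysed as randomised, and is not removed on eligibility grounds. This leaves the clinical reasons for stopping treatment untouched.

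The cost is some protocol wording and a brief contact with each listed patient. A few patients will move to a later list. Where that takes a list below two groups, the draw is somewhat delayed and the others wait longer.

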#### **3.2. Number of participants and intervention**

Inclusion will progress until about 120 participants are enrolled into this trial. The participants who will be randomized into two groups; and allocated to either:

1. Group 1 (G1) with start of weekly treatment in active structured skills training group therapy lasting for 14 weeks, following the Norwegian translation of the Swedish version of the ADHD skills training manual/workbook (Hirvikoski 2011; Morgensterns 2015) based on an adaption of Marsha Linehan's dialectical behavior therapy (DBT) for borderline personality disorder. The groups embrace 7 - 10 participants, and two group leaders trained in group therapy, cognitive behavioral treatment or DBT. Each session contains an initial short repetition and feedback on the previous session, followed by review of the homework during the first hour. After a break, a new topic with exercises and homework for the following week is introduced.

2. Group 2 (G2) with treatment as usual/clinical management for the first 14 weeks, followed by delayed admission to the active intervention of structured skills training group therapy (partial cross-over).

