## 5. INVESTIGATIONAL INTERVENTION

### 5.1. Elements of the DBT-based group therapy

The structured skills group treatment uses elements from DBT such as psychoeducation, acceptance, mindfulness, and functional behavioral analysis, such targeting symptoms and functional problems common in ADHD. It consists of 14 weekly group sessions, each lasting two hours separated by a 15-minute break. Each group includes 7-9 patients with ADHD and two therapists. Group sessions follow a structure with manualized instruction for the therapists and workbook for the patients.

A typical session begins with introducing a new mindfulness exercise performed together in the group. The first part of the session then focuses on feedback on last week's homework of skill training, while the second part introduces a new topic and related homework for the next week. The topics for the different sessions include psychoeducation, mindfulness, functional behavioral analyses, and how to understand and manage different symptoms and aspects of ADHD, e.g. impulsivity, addiction, emotional

regulation, self-esteem, and relation to others. Interaction between the participants is important, and the therapists should encourage and balance their feedback and discussion during the session. After each group session, patients will receive 15-20 minutes of individual coaching with one of the therapists. This is an add-on element according to a Swedish adaptation of the program. The coaching focuses on adherence to homework related to each participant's situation and pre-defined goals.

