## **5.2. The arm of treatment as usual condition**

The control condition of treatment as usual (TAU) was not standardized but rather defined as the clinical management/ treatment that the patient would have received if not included in the project. Some patients will be able to receive drug treatment, while others receive psychoeducation alone or in combination with medication. It could thus vary between both individuals and clinics. A survey will be made of what the patients have received from "treatment as usual" before they enter the psychotherapeutic group treatment.

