### **10.3. Statistical analysis**

Collected data will be analyzed with SPSS (PASW statistics). Descriptive statistics is used for testing potential differences between the groups at baseline (chi-square tests for categorical variables, independent samples t-tests for continuous variables). We use independent samples t- tests to compare the mean difference of change from pre- to post-treatment between the two treatment groups, and analyses of covariance (ANCOVA) to compare these differences while adjusting for variables that differed between the groups at baseline as covariates. For the non-controlled extension part of the study, we use paired sample t-tests to assess change from baseline to 6-months follow-up, and analyses of variance (ANOVA) for repeated measures to assess change in symptom scores from baseline to post-treatment from the RCT and at 6 months follow-up after group treatment for all participants. We will estimate standardized effect sizes (ES) of the treatment by dividing the mean difference in symptom scores from pre-to post treatment with the pooled standard deviation (SD) of the respective measure, reporting as Cohen's d. The significance threshold is set at 5% (two-tailed) and we use two-sided 95% confidence intervals (CI). Analyses are restricted to participants with actual responses on each of the respective questionnaires, i.e., will exclude participants with missing values analysis-by-analysis.

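### Allocation is blocked by lottery draw within site, but the between-arm analysis names neither site nor draw, so shared draw differences stay in its standard error and the test is mildly conservative

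*Protocol*

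**What the plan says.** **Allocation (protocol, 10.2).** "Participants are randomly allocated (ratio 1:1) to either the active DBT-bGT or the control TAU condition by a blinded lottery procedure at each site". The lottery is held "When the list is fully subscribed with a sufficient number of participants to form two groups", and "one number at a time is drawn by an independent person every second time to the DBTgroup and the TAU-goup respectively". The arms therefore have equal numbers in every draw, or differ by one. This is restricted randomisation with the site-draw as the block.

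**Block size.** Section 3.2 says "The groups embrace 7 - 10 participants, and two group leaders trained in group therapy"; section 5.1 says "Each group includes 7-9 patients with ADHD and two therapists". Two groups per draw means about 14–20 patients. The protocol does not give the number of sites or draws. Blocking by site is explicit. More than one draw per site is an inference from the full-list rule and from the stated aim of keeping the arms balanced over time.

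**Analysis (protocol, 10.3).** "We use independent samples t- tests to compare the mean difference of change from pre- to post-treatment between the two treatment groups". An ANCOVA follows, with covariates selected by whether the arms differ on them at baseline. No model contains site or draw.

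**The concern.** An analysis should reflect the restrictions under which patients were allocated. Here each draw gives half its patients to each arm, so anything that shifts the change scores of everyone in a draw (the clinic, the season, the local case mix) drops out of the treatment difference. The pooled t-test does not know this and counts that variation as noise.

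The covariate rule cannot repair the mismatch. It admits a variable only when the arms are unequal on it, and the lottery makes the arms equal on site and draw. It thus shuts out the factors that the design controls.

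At stake are a confidence interval wider than the design warrants and a test that runs below its nominal 5% level.

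**Working it through.** **1. The plan's own sample size.** Inputs from 10.1: difference 10, SD 15, two-sided alpha 0.05, power 0.90. The standard formula for two means gives n = 2 × (1.960 + 1.282)² × (15/10)² ≈ 47.3, so 48 per arm (stated: about 50). Allowing 20% dropout, 96/0.8 = 120, as stated. The check below uses 96 evaluable patients.

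**2. Number of draws.** 120/(2 × 10) = 6.0 and 120/(2 × 7) = 8.6, so about 6–9 draws. A fixed factor for draw uses 5–8 degrees of freedom. The t-test has 96 − 2 = 94.

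**3. Standard error.** Let ρ be the share of the variance in *change* that lies between site-draws. With equal arms in every draw:

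- true SE = 15 × √(2(1 − ρ)/48)
- t-test SE ≈ 15 × √(2/48) = 3.06
- ratio ≈ 1/√(1 − ρ)

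The protocol does not give ρ, so it is assumed over a range from 0 to 0.20.

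**4. Simulation.** 20,000 trials per setting, total SD 15, true difference 0 or 10, six draws of 8 + 8. The unstratified t-test is compared with a model that adds a fixed effect for draw.

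| ρ (assumed) | SE excess, formula | Mean SE: t-test / with draw | Type I error: t-test / with draw | Power: t-test / with draw |
|---|---|---|---|---|
| 0 | 0% | 3.059 / 3.059 | 0.048 / 0.048 | 0.897 / 0.897 |
| 0.01 | 0.5% | 3.058 / 3.045 | 0.048 / 0.049 | 0.900 / 0.902 |
| 0.05 | 2.6% | 3.047 / 2.983 | 0.047 / 0.052 | 0.906 / 0.912 |
| 0.10 | 5.4% | 3.038 / 2.903 | 0.043 / 0.053 | 0.914 / 0.928 |
| 0.20 | 11.8% | 3.015 / 2.738 | 0.032 / 0.050 | 0.932 / 0.954 |

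Three notes on reading the table:

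- The simulation error of a type I rate near 0.05 is √(0.05 × 0.95/20,000) ≈ 0.0015. The 1% row is therefore not distinguishable from nominal, and small departures in the draw-adjusted column are noise. Seven draws of 7 + 7 give t-test type I errors of 0.049, 0.044 and 0.041 at 1%, 5% and 10%: the same pattern.
- With only six draws the formula slightly overstates the excess. The simulated mean SEs give 3.047/2.983 = 1.021 at 5% and 3.038/2.903 = 1.046 at 10%.
- Power rises with ρ in both columns because total SD is held at 15 and the between-draw part cancels from the estimate.

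**5. The opposing effect.** The DBT arm is treated in therapy groups, which the table leaves out. With an assumed therapy-group correlation of 0.05 and groups of 8, the variance ratio is [(1 + 7 × 0.05) + 1]/2 = 1.175. The naive SE is then 1/√1.175 = 0.92 of the true one, about 8% too small.

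**The case against.** The strongest case on the other side is that the consequence is small and on the safe side. At a 5% share the t-test gives up 0.6 points of power and false positives do not increase. With equal arms in every draw, the point estimate is the same with or without the draw term; only the reported interval is too wide. All of this stands.

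The share is also unknown and may be near zero. The plan tests change, which already removes stable differences in level between sites, so only differences between draws in how much patients change can matter. This stands too, and is why the range starts at 0.

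A reader might cite section 5.2, which says of usual care that "It could thus vary between both individuals and clinics", as evidence that the share is large. It does not show that. Variation in the control condition alone makes the treatment difference vary between sites; it does not establish a shared level that cancels between the arms. If sites are regarded as a random sample, such variation would make the naive standard error too small.

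A reader might also infer that the t-test's standard error is too large overall. The documents do not support that. Therapy-group clustering pulls the other way and could outweigh the effect described here, so the net direction is not known.

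What does not stand is that the matter is simply left to a statistical analysis plan. Section 10.3 fixes both the test and the rule for choosing covariates, and as written these do not match section 10.2.

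**Conclusion.** The mismatch between allocation and analysis is real, and its effect is modest. Taken alone, it makes the reported standard error too large by about 0.5%, 2.6% or 5.4% when site-draw explains 1%, 5% or 10% of the variance in change. About 0.2, 0.6 or 1.4 points of power are given up, and the test is slightly conservative. At zero share nothing is lost.

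It would be tempting to conclude that the trial is underpowered or that patients are wasted. Neither follows. Power stays at about 90% or more at the assumed effect. The equivalent of roughly 1%, 5% or 11% more patients, from 1/(1 − ρ) − 1, describes the width of the reported interval; the estimate itself is no less precise.

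The result rests on the assumed share, on near-equal arms per draw among the patients analysed, on draws of about 14–20 patients inferred from the group sizes, and on setting therapy-group clustering aside. The change is worth making because it aligns the analysis with the design at almost no cost.

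**What to change.** State in section 10.3 that site-draw, or at least site, is a prespecified fixed factor in the week-14 between-arm model for every outcome, whether or not the arms differ on it at baseline. Record the site and draw for each patient; the code list that each site keeps under 10.2 is a natural place.

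The cost is one sentence, one identifier per patient and about 5–8 of roughly 94 degrees of freedom. The simulation shows no visible loss of power when draws do not differ at all (0.897 with either analysis). Section 10.1 allows for up to 20% dropout and section 10.3 drops missing responses analysis by analysis, so the arms may be less than perfectly balanced within draws among those analysed. The factor also protects against that.

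This term does not deal with therapy-group clustering in the DBT arm. That is a separate issue, and any model for it would be a separate decision with its own cost in degrees of freedom.
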